**Recruitment & Retention Pilot.** This pilot study will utilize a randomized controlled trial design to evaluate two components of behavioral economic strategies to improve recruitment and retention. To be eligible for the pilot study participants must meet all eligibility criteria for one of the four participating studies (828958, 824061, **824860**, 828125), have a phone capable of receiving SMS messages, and consent to receive SMS messages. ~576 participants will be enrolled across the four participating research studies. All subjects will receive standard text messages and will be randomized to one of four groups (blocked within each study to ensure balanced groups): (1) Standard recruitment (SR): subjects will receive text messages ~2 days prior to their Intake visit with relevant information about the time, date, and location of the visit as well as contact information for study staff ("You have a study visit on [Date] at [Time]. Visit comp is \$10. Reply Y to confirm. See <http://j.mp/2222222> for reminders. Reply or appt may be canceled."); (2) SR + Information Provision (IP): Subjects will receive personalized messages designed to target injunctive norms regarding participating in research (e.g., "[Name], wondering why you should volunteer for research? Many find it a rewarding way to advance science and be a part of a community <http://j.mp/2222222>."); (3) SR + Contingency Management (CM): CM will be provided in the form of a randomization table with a high proportion of numbers that correspond to "chips" with little (\$1) monetary value. Participants draw by choosing numbers between 1-500 upon completion of an objectively verified target behavior (e.g., attending an Intake visit), and bonuses are often provided for continued performance. A similar strategy has been successful in augmenting visit compliance in several treatment studies. All text reminders will be delivered using the Way 2 Health (W2H) software platform. Upon completion of all requirements for a given visit, participants will receive 5 lottery "draws" for that visit. Attendance at all visits earns participants bonus draws upon completion of the study. Failure to attend a visit without prior approval or failure to complete all visit requirements results in no draws for that visit. The lottery contains 500 "chips" (numbers that correspond to monetary values within a table): 250 have a value of \$0, 219 have a value of \$1, 30 have a value of \$5, and 1 has a value of \$100. The study completion bonus will be 5 extra draws. Thus, at each visit, subjects will have the opportunity to make 5 draws, for maximum possible earnings of \$120; (4) SR + IP + CM (IC): In this group, subjects will receive the targeted text messages and receive CM. The design of our study allows us to examine each strategy independently as well as combined to evaluate the optimal approach.

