## 2. Statistical Analysis

### **Power Analysis and Sample Size.**

Our study is a longitudinal between-subject design that seeks to test the following hypotheses: 1) that HIV+ smokers experience larger abstinence-induced cognitive deficits than HIV- smokers (Aim 1); 2) have lower quit-rates than HIV-smokers following standard treatment (Aim 2); and 3) that the association between HIV status and relapse is mediated by abstinence-induced cognitive deficits (Aim 3). We have designed our study to achieve 80% power, testing at a global  $\alpha=0.05$  for each of the hypothesis families (Figure 1). Our sample size of 300 was determined primarily by Aim 2. Based on prior work, we expect a ~15% difference in abstinence rates between HIV+ and HIV- smokers (Ferketich et al., 2013; Humfleet et al., 2013; Matthews et al., 2013; Silagy et al., 2004). With 150 HIV+ vs. 150 HIV- smokers, we have 80% power to detect a difference of ~15 percentage points in point-prevalence abstinence (60% vs. 45%, 50% vs. 35%, 40% vs. 25%), using a z-test on log-odds with a type 1 error of 5%. For Aim 1, we will test the HIV status by abstinence condition (24-h abstinence vs. smoking-as-usual) interaction for 5 cognitive measures using a linear regression with one between- and one within-subjects factor. We will correct for 5 tests using  $\alpha=0.01$ . We have 80% power to detect medium effect sizes (Cohen's  $d=0.4$ ). For Aim 3, we will test whether abstinence-induced cognitive deficits predict quit rates and, using SEM, test whether cognitive deficits mediate the effect of HIV status on quitting. The primary aim will be to test the overall fraction of the effect mediated, which will be tested at  $\alpha=0.05$ , which gives 80% power to detect small to medium effects ( $d=0.32$ ). For our exploratory aim, the component individual deficits will be treated as secondary and tested individually as part of an exploratory analysis, also with a 5% type 1 error. To characterize cognitive deficits in HIV+ smokers, 150 subjects will give us an estimate for each measure with a 95% CI that is 0.32 standard deviations wide (Upper – Lower limits). We will estimate the within-subject correlation for these as repeated measures, with a 95% CI that is 0.32 wide (Upper – Lower) if  $r=0$ , 0.24 if  $r=0.5$ , and 0.14 if  $r=0.75$ . Power was calculated using PASS software, NCSS, Kaysville, UT.

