### **Recruitment & Retention Pilot:**

Power is provided for our primary aim. The analysis will compare the enrollment rates between the four intervention arms, and examine main and interaction effects. For SR arm, we expect a 28% of subjects who schedule an Intake will be eligible and enroll (based on existing data across the four studies). With the proposed sample of 576, we have >80% power ( $\alpha=.05$ ) to detect a difference between the SR arm and the IP and CM arms of 12%, corresponding to an OR of 1.75. For the interaction term, we have 80% power ( $\alpha=.05$ ) to detect a departure from additivity of the main effects corresponding to a ratio of odds ratios (ORR) of 5.5.

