### **Power Analysis, Sample Size and Data Analysis Rhythm Monitoring Sub-Study.**

#### Sample Size.

Our study is a longitudinal between-subject design that seeks to test the following hypotheses: 1) that HIV+ smokers have higher AF burden than HIV- smokers (Aim 1); 2) AF burden will be associated with worse cognitive function (Aim 2) and more depressive symptoms (Aim 3); and 3) that the association between AF burden and cognition and depression will be strong among HIV-infected smokers. Our sample size of 50 participants was determined primarily by Aim 1. Because we are interested in AF burden (a continuous measure) rather than a diagnosis of AF, we have 80% power to detect a medium to large effect size ( $d=0.7$ ), using a t-test with a type 1 error of 5%. For Aims 2 and 3, we have 80% power to detect a correlation of  $r=0.4$  between AF burden and cognition and depressive symptoms, with  $\alpha=0.01$  to correct for multiple outcomes. The current pilot data will be used to derive effect size estimates to support a larger clinical study.

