#### Data Analysis.

Descriptive statistics (mean, median, standard deviation, skewness, frequency, etc) will be provided for each outcome measure from the rhythm monitoring device and for the sample characteristics (age, sex). Log-transformation will be considered for continuous outcomes with skewed distributions. Multiple comparisons will be corrected and 5% type I error will be maintained to guard against the problem of false positives due to multiple testing.

Aim 1 will use linear regression with AF burden as the primary outcome and HIV status as a between-subjects factor. Cross-sectional associations between arrhythmia burden and cognitive function (Aim 2) and depression indices (Aim 3) at baseline will be assessed using multivariable linear regression with HIV status as a between-subjects factor. All models will include relevant covariates (e.g., smoking rate, age, sex). For our exploratory aim, longitudinal associations between arrhythmia burden and cognitive and psychiatric measures will be assessed using multivariable linear regression relating a) arrhythmia at baseline and b) changes in arrhythmia burden to changes in cognitive function/psychiatric measures. We will test the HIV status by time interaction and include a dichotomous variable for smoking status at end-of-treatment (abstinent vs. relapsed).

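### Rhythm sub-study Aims 2 and 3 have 63% power (72% one-sided) at the stated alpha, not 80%; the pilot's interaction figure and the planned cognitive-change analysis also need correcting

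*Combined protocol and SAP*

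**What the plan says.** **Rhythm sub-study, Sample Size.** The sample is 50 (25 HIV+, 25 HIV-), sized mainly for Aim 1. For that aim "we have 80% power to detect a medium to large effect size", d=0.7, by t-test with 5% type 1 error. Then: "For Aims 2 and 3, we have 80% power to detect a correlation of" r=0.4 between AF burden and cognition or depressive symptoms, at alpha=0.01 "to correct for multiple outcomes". No sidedness is given. The accrual section for this sub-study enrols 60 in order to have 50 with usable data.

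**Recruitment & Retention Pilot.** Participants "will be randomized to one of four groups", about 576 in all and balanced. The power section expects 28% enrolment under standard recruitment (SR) and claims more than 80% power "to detect a difference between the SR arm and the IP and CM arms of 12%, corresponding to an OR of 1.75". For the interaction it claims 80% power for a departure "corresponding to a ratio of odds ratios (ORR) of 5.5".

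**Rhythm sub-study, Data Analysis.** An exploratory longitudinal analysis relates, among other things, "changes in arrhythmia burden to changes in cognitive function/psychiatric measures". The design section puts the second recording at weeks 8-10. Table 1 marks every neurocognitive task at Lab 1 and Lab 2 only.

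**The concern.** A multiplicity-corrected alpha of 0.01 is strict for 50 people and a correlation of 0.4, so the 80% looked too high. If it is, a null result for AF burden and cognition or depression would be credited with more evidential weight than it has. That matters because the sub-study is meant to supply effect sizes for a larger study.

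The pilot figure looked wrong in the opposite direction: 5.5 is a very large ratio for 144 per arm, so a reader would conclude that only an extreme interaction could be found.

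The change analysis appeared to need a cognitive measurement that the schedule does not contain.

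**Working it through.** **1. Correlation, Aims 2 and 3.** Inputs from the Sample Size section: n=50, r=0.4, alpha=0.01. Power = Φ(atanh(r)·√(n−3) − z).

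atanh(0.4)·√47 = 0.4236 × 6.856 = 2.904.

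| Test | z | Power |
|---|---|---|
| alpha 0.01, two-sided | 2.576 | Φ(0.329) = 62.9% |
| alpha 0.01, one-sided | 2.326 | Φ(0.578) = 71.8% |
| alpha 0.05, two-sided | 1.960 | Φ(0.944) = 82.8% |

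Simulation of the correlation test gave 63.4% and 72.6% for the first two rows. The stated 80% is not reproduced at alpha=0.01 on either sidedness.

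Detectable r at 80% power is tanh((z + 0.842)/√47): 0.46 two-sided, 0.43 one-sided. The n needed for r=0.4 is ((z + 0.842)/0.4236)² + 3: 68.1, so 69, two-sided; 58.9, so 59, one-sided. If all 60 enrolled were usable, power would be 73.3% two-sided and 80.8% one-sided.

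**2. Aim 1.** t-test, 25 v 25, d=0.7, 48 degrees of freedom, noncentrality 0.7·√12.5 = 2.475. Power is 67.9% two-sided and 78.7% one-sided. For 80% power, d must be 0.81 two-sided or 0.71 one-sided.

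The main study does not settle the convention. Its Aim 1 says "We have 80% power to detect medium effect sizes" (d=0.4 at alpha=0.01). With 150 v 150 the detectable d is 0.40 two-sided and 0.37 one-sided. Its d=0.32 at 0.05 also fits two-sided (0.32 v 0.29). The main study's quit-rate pairs, however, give 74% to 79% two-sided and 83% to 87% one-sided on a log-odds z-test.

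**3. Pilot.** 576/4 = 144 per arm; SR rate 28%; 28% + 12 points = 40%, an odds ratio of 1.71 (ln = 0.539). All tests here are two-sided at 5%.

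*Main effect*, log-odds z-test, SE = √(1/(n₁·0.28·0.72) + 1/(n₂·0.40·0.60)):
- Factorial margins, 288 v 288, other factor assumed to have no effect: SE 0.178; Φ(3.028 − 1.960) = 86%.
- One arm v SR, 144 v 144: SE 0.252; Φ(2.141 − 1.960) = 57%.

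*Interaction*, Wald test on the log ratio of odds ratios, with variance the sum of 1/(144·p(1−p)) over the four cells. The documents do not give the main effects assumed for this calculation, so I took main-effect odds ratios from 1 to 1.75.
- Example with both main effects at 1 and a ratio of 2.76: the combined cell has p=0.518, SE 0.362, ln(2.76)/SE = 2.803, power 80%.
- Over the whole range, 80% power is reached at 2.7 to 2.8 for ratios above 1, and at 2.7 to 3.2 (as the inverse) for ratios below 1.
- At 5.5, power is at least 99%; at 1/5.5, at least 96%.
- A ratio of 5.5 at 80% power corresponds to about 53 to 60 per arm, not 144.

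**4. Change in cognition.** N-back, Stroop, HVLT, stop task and delay discounting are marked at Lab 1 (week 1) and Lab 2 (week 2). The End of Treatment visit collects smoking rate, CO and questionnaires. The second recording is at weeks 8-10, so no tested cognition falls at or after it. The Lab 1 to Lab 2 difference cannot stand in: it is a counterbalanced contrast of abstinence with usual smoking, completed before that window. The documents give two first-recording windows (weeks 2-4 in the design section, weeks 0-2 in the AF burden section), but neither adds a later test. HADS and PAOFI are marked at every visit from Lab 1 to end of treatment.

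**The case against.** The best defence is a one-sided reading. The sub-study hypotheses are directional and its effect sizes are given to one decimal. One-sided, the detectable values are d=0.71 and r=0.43, which round to the stated 0.7 and 0.4; two-sided (0.81 and 0.46) neither does. On that reading Aim 1 is essentially right and the gap for Aims 2 and 3 is about 0.03 in r. This deserves weight, and is why both values are given throughout. But power at r=0.4 is still 72%, and no one-sided test is stated. The one combination that reaches 80% (60 participants, one-sided) uses the enrolled number; the plan makes 50 the usable sample.

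The cause of the error is unknown. The 80% claim would hold at an uncorrected two-sided 5%, but the documents do not show that this is what happened.

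On the pilot, the plan says it will examine main and interaction effects, so the factorial reading is natural and the 57% is a point about wording. The 5.5 figure is conservative: the pilot is more sensitive than stated.

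The change analysis is exploratory, and its wording does not confine cognition to performance tests. Besides PAOFI, the PROMIS cognitive form is also repeated after Lab 2. All of this limits the seriousness. It does not make the figures right or supply the missing tests.

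**Conclusion.** The concern holds. At n=50 and alpha=0.01, power for r=0.4 is 63% two-sided or 72% one-sided, against a stated 80%. This rests on a bivariate-normal correlation and on 50 usable participants.

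Aim 1 is a matter of unstated sidedness: 68% or 79% at d=0.7. The pilot's 5.5 should be about 2.7 to 3.2, given a 28% base rate, equal arms and main-effect odds ratios of 1 to 1.75. Its main-effect claim is correct for the margins only. Change in tested cognition up to the second recording cannot be computed; change in psychiatric and self-reported measures can.

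These points should be corrected, but they are confined to the sub-study and the pilot.

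**What to change.** - **Sub-study Aims 2 and 3:** state 63% power for r=0.4 at two-sided alpha=0.01, or give the detectable r as 0.46 (0.43 if one-sided).
- **Sub-study Aim 1:** state the sidedness. Two-sided, d=0.7 has 68% power and 80% needs d=0.81; one-sided, it has 79%.
- **Pilot:** replace 5.5 with about 2.8 (range 2.7 to 3.2) and state the assumed main effects and direction. Say that the power above 80% refers to the factorial margins (288 v 288, 86%) and that a single arm against SR has about 57%.
- **Change analysis:** limit it to measures repeated through treatment: HADS for psychiatric symptoms and PAOFI for self-reported cognitive function. PROMIS could be added if its schedule suits. Keep tested cognition for the baseline cross-sectional analysis. Label this change of outcome as made after sub-study recruitment ended in March 2020.

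The cost is text only. The repeated measures are already scheduled, so no visits or participants are added. With recruitment closed, the power shortfall can be reported correctly but not made up.

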#### Data Analysis.

Descriptive statistics (mean, median, standard deviation, skewness, frequency, etc) will be provided for each outcome measure from the rhythm monitoring device and for the sample characteristics (age, sex). Log-transformation will be considered for continuous outcomes with skewed distributions. Multiple comparisons will be corrected and 5% type I error will be maintained to guard against the problem of false positives due to multiple testing.

Aim 1 will use linear regression with AF burden as the primary outcome and HIV status as a between-subjects factor. Cross-sectional associations between arrhythmia burden and cognitive function (Aim 2) and depression indices (Aim 3) at baseline will be assessed using multivariable linear regression with HIV status as a between-subjects factor. All models will include relevant covariates (e.g., smoking rate, age, sex). For our exploratory aim, longitudinal associations between arrhythmia burden and cognitive and psychiatric measures will be assessed using multivariable linear regression relating a) arrhythmia at baseline and b) changes in arrhythmia burden to changes in cognitive function/psychiatric measures. We will test the HIV status by time interaction and include a dichotomous variable for smoking status at end-of-treatment (abstinent vs. relapsed).

### **3. Confidentiality**

All subject information will be kept in a secure filing cabinet that is accessible only to authorized study personnel. All databases containing subject information will be password protected, and again, accessible only to authorized study personnel. Each subject will have a unique study ID number for all data collected. In all data sets we will use ID numbers, only. A separate data set linking names with ID numbers will be accessible only by the senior project staff. All communications about subjects will use the ID number only and never include names or other personal information. All data will be stored until all analyses are completed. No data will be shared with any unauthorized party (i.e., aside from study personnel and regulatory officials). Any publication of data will not identify subjects by name or with an identifier that could be used to reveal identity.

Data collected in MS Access and REDCap databases will be stored on a secure server administered by the Penn Medicine Academic Computing Services (PMACS) organization and will be restricted to only those individuals who are authorized to work on the trial. Individual user accounts with passwords will be used to restrict access to the database. Specific privilege assignments will also be employed so a user has access only to the functions necessary to complete applicable operations appropriate for their role in the trial. Additional measures to prevent unauthorized external access to the database

environment will be employed using network firewall technologies. The Data Manager will maintain the database in an appropriate manner for the retention period required by regulation. Database administration includes user account maintenance, database security, performance monitoring, and database change management. Daily backups are performed to protect data against accidental destruction or corruption.

Remote study sessions will be conducted via phone or via BlueJeans, which is a HIPAA-compliant platform with security features including a room lock to ensure that communications within the platform remain private.

Data will be accessible the study Principal Investigator, Co-Investigators, the Study Physician, other study staff and the UPenn IRB and Office of Human Research.

iRhythm Technologies Inc. will retrieve and process the stored ECG data from the rhythm monitoring device. These data will be transmitted to study investigators at the University of Pennsylvania for analysis. The participant study identification number will be the only identifier utilized. Participants will receive immediate notification of any serious arrhythmias discovered by the study staff and will be encouraged to follow up with their PCP.

How will confidentiality of data be maintained? Check all that apply.

- Paper-based records will be kept in a secure location and only be accessible to personnel involved in the study.
- Computer-based files will only be made available to personnel involved in the study through the use of access privileges and passwords.
- Prior to access to any study-related information, personnel will be required to sign statements agreeing to protect the security and confidentiality of identifiable information.
- Whenever feasible, identifiers will be removed from study-related information.
- A Certificate of Confidentiality will be obtained, because the research could place the subject at risk of criminal or civil liability or cause damage to the subject's financial standing, employability, or liability.
- A waiver of documentation of consent is being requested, because the only link between the subject and the study would be the consent document and the primary risk is a breach of confidentiality. (This is not an option for FDA-regulated research.)
- Precautions are in place to ensure the data is secure by using passwords and encryption, because the research involves web-based surveys.
- Audio and/or video recordings will be transcribed and then destroyed to eliminate audible identification of subjects.
- Other (specify):

The PMACS will be the hub for the hardware and database infrastructure that will support the project and is where the W2H web portal is based. W2H uses a role-based access control (RBAC) approach to assure that participant confidentiality and study integrity is preserved. The PMACS provides a secure computing environment for a large volume of highly sensitive data.

#### **4. Subject Privacy/Protected Health Information**

The following personal health information will be collected as part of this study:

- Name, address, telephone number, email address
- Date of birth
- Social Security Number (W-9 form)
- Some personal information that may be considered sensitive, such as medical history, psychological history, alcohol use history, etc.
- Results from physical examinations, tests or procedures, including urine drug screening
- Information on smoking, cognition, or HIV-related biomarkers from the urine and blood samples provided at the Intake Session
- Medical Record Number
- Results from HIV testing for individuals who must have their HIV status confirmed on-site
- Results from cardio rhythm monitoring (if applicable)

Every possible precaution, as described above, will be taken to ensure that the privacy of subjects' personal health information will be maintained. Potential participants will be contacted over the phone after responding to recruitment advertisements. Participants will undergo an initial phone screening where preliminary eligibility for the research study will be determined. Only if a participant is initially eligible, will they complete Intake tasks, remotely or in-person, to confirm eligibility. All in-person screenings and participant sessions will be conducted in private rooms with a trained member of the research staff. All data collected over the phone or in-person will be collected by research staff who have completed the CITI Protection of Human Subjects Research Training as well as HIPAA Compliance Training. Information will never be recorded with identifiers other than study ID. Results will not be communicated to other personnel or to the subjects. Data will be accessible to the Study Investigators, Study Physician, study staff, UPenn IRB, Office of Clinical Research, authorized UPenn staff (e.g. accounting and billing matters, provide treatment, etc.).

